#### **6.1.5. Visit 5: Day 37 (7 to 11 Days After Visit 4)**

- Review the subject's e-diary data and remind the subject to continue completing the e-diary up to Day 14.
- Ensure that the subject continues to be eligible for the study and does not meet any of the withdrawal criteria as described in [Section 6.5](#).
- Based on clinical evaluation, determine whether any AEs or SAEs have occurred since the last study visit. Record and report findings as described in [Section 8](#) and the [Schedule of Activities](#). Review AEs that were ongoing from the previous visit and record their stop dates or confirm if they are still continuing.
- Record nonstudy vaccines and concomitant medications as described in [Section 5.8.1](#).
- Conduct a targeted physical examination, including vital signs if appropriate, evaluating any clinically significant abnormalities based on history and the participant's self-reported symptoms or complaints since the last visit. Abnormal results, including those that indicate worsening of medical history conditions, must be recorded on source documents and the AE CRF (with recording of time relative to vaccination) as appropriate.
- Collect a blood sample of approximately 20 mL for immunogenicity testing ([Section 7.2](#)).
- Ask the subject to contact the site staff or investigator immediately, to determine if an unscheduled visit is required, if he or she experiences any of the following:
  - Fever  $\geq 39.0^{\circ}\text{C}$  ( $\geq 102.1^{\circ}\text{F}$ ).
  - Redness or swelling at the injection site measuring greater than 10 cm ( $\geq 21$  measuring device units).
  - Any peeling/scaling or blackening of the skin at the injection site.
  - Severe arm pain.
  - Any severe systemic event within 14 days following vaccination.
  - If any new, late-onset reaction occurs from the previous vaccination.
  - If any ongoing reaction from the previous vaccination worsens.
- Ask the subject to contact the site staff or investigator immediately if any significant illness or hospitalization occurs.

- Schedule an appointment for the subject to return for the next study visit.
- Remind the subject to bring the completed e-diary to the next visit.
- Complete the source documents.
- Complete the CRF.

#### **6.1.6. Visit 6: Month 2 (25 to 35 Days After Visit 4)**

- Review the subject's e-diary data after Dose 3 and follow up on any ongoing local reactions or systemic events.
- Collect the subject's e-diary.
- Ensure that the subject continues to be eligible for the study and does not meet any of the withdrawal criteria as described in [Section 6.5](#).
- Based on clinical evaluation, determine whether any AEs or SAEs have occurred since the last study visit. Record and report findings as described in [Section 8](#) and the [Schedule of Activities](#). Review AEs that were ongoing from the previous visit and record their stop dates or confirm if they are still continuing.
- Record nonstudy vaccines and concomitant medications as described in [Section 5.8.1](#).
- Conduct a targeted physical examination, including vital signs if appropriate, evaluating any clinically significant abnormalities based on history and the participant's self-reported symptoms or complaints since the last visit. Abnormal results, including those that indicate worsening of medical history conditions, must be recorded on source documents and the AE CRF (with recording of time relative to vaccination) as appropriate.
- Collect a blood sample of approximately 20 mL for immunogenicity testing ([Section 7.2](#)). An additional blood sample of approximately 40 mL will be obtained.
- Ask the subject to contact the site staff or investigator immediately if any significant illness or hospitalization occurs.
- Schedule an appointment for the subject to return for the next study visit.
- Complete the source documents.
- Complete the CRF.

#### **6.1.7. Visit 7: Month 4 (80 to 100 Days After Visit 4)**

- Ensure that the subject continues to be eligible for the study and does not meet any of the withdrawal criteria as described in [Section 6.5](#).

- Based on clinical evaluation, determine whether any newly diagnosed chronic medical conditions or SAEs have occurred since the last study visit. Record and report findings as described in [Section 8](#) and the [Schedule of Activities](#). Review AEs that were ongoing from the previous visit and record their stop dates or confirm if they are still continuing. In addition, any AEs occurring up to 48 hours after the blood draw will be recorded.
- Conduct a targeted physical examination, including vital signs if appropriate, evaluating any clinically significant abnormalities based on history and the participant's self-reported symptoms or complaints since the last visit.
- Collect a blood sample of approximately 20 mL for immunogenicity testing ([Section 7.2](#)).
- Ask the subject to contact the site staff or investigator immediately if any significant illness or hospitalization occurs.
- Schedule an appointment for the subject to return for the next study visit.
- Complete the source documents.
- Complete the CRF.

#### **6.1.8. Visit 8: Month 7 (165 to 195 Days After Visit 4)**

- Ensure that the subject continues to be eligible for the study and does not meet any of the withdrawal criteria as described in [Section 6.5](#).
- Based on clinical evaluation, determine whether any newly diagnosed chronic medical conditions or SAEs have occurred since the last study visit. Record and report findings as described in [Section 8](#) and the [Schedule of Activities](#). Review AEs that were ongoing from the previous visit and record their stop dates or confirm if they are still continuing. In addition, any AEs occurring up to 48 hours after the blood draw will be recorded.
- Conduct a targeted physical examination, including vital signs if appropriate, evaluating any clinically significant abnormalities based on history and the participant's self-reported symptoms or complaints since the last visit.
- Collect a blood sample of approximately 20 mL for immunogenicity testing ([Section 7.2](#)).
- Ask the subject to contact the site staff or investigator immediately if any significant illness or hospitalization occurs.
- Schedule an appointment for the subject to return for the next study visit.
- Complete the source documents.
- Complete the CRF.

### **6.1.9. Visit 9: Month 13 (340 to 380 Days After Visit 4)**

- If study-level unblinding following the third interim analysis has already occurred ([Section 5.3](#)), use the IRT system to determine if the subject received *C difficile* vaccine (not placebo) at Doses 1, 2, and 3. If the subject received *C difficile* vaccine (at either antigen dose level of 100 µg or 200 µg), obtain consent for the subject to enter the extension stage ([Section 6.3](#)).

**For subjects entering the extension stage, follow the procedures in [Section 6.3.1](#) rather than the procedures listed below. For the subjects not entering the extension stage, complete the procedures below.**

- Review AEs that were ongoing from the previous visit and record their stop dates or confirm if they are still continuing. In addition, any AEs occurring up to 48 hours after the blood draw will be recorded.
- Conduct a targeted physical examination, including vital signs if appropriate, evaluating any clinically significant abnormalities based on history and the participant's self-reported symptoms or complaints since the last visit.
- Collect a blood sample of approximately 20 mL for immunogenicity testing ([Section 7.2](#)).
- Ask the subject to contact the site staff or investigator immediately if any significant illness or hospitalization occurs.
- Complete the source documents.
- Complete the CRF.

## **6.2. Month 0, 1, and 6 Regimen**

### **6.2.1. Visit 1: Day 1 - Vaccination 1**

- Obtain written informed consent prior to performing any protocol-required procedures.
- Record the subject's demography (including date of birth, sex, race, and ethnicity).
- Record medical history of significance, including the presence of chronic conditions and relevant surgical procedures.
- Record nonstudy vaccines and concomitant medications as described in [Section 5.8.1](#).
- Perform a physical examination evaluating any clinically significant abnormalities within the following body systems: general appearance, skin, head/eyes/ears/nose/throat, heart, lungs, abdomen, extremities, neurological, and lymph nodes. Abnormal results must be recorded on source documents and the medical history CRF.

- Perform vital sign measurements, including weight, height, sitting blood pressure, sitting pulse rate, and respiratory rate. When multiple measurements are taken for the same time point, the most out-of-range (eg, highest or lowest) value must be reported. (See the SRM for guidance.)
- Measure and record the subject's oral temperature.
- Ensure that all inclusion criteria, none of the exclusion criteria, and none of the temporary delay criteria are met ([Section 4](#)).
- An appropriate site staff member (may be blinded or unblinded) will use the IRT system to obtain the subject's randomization number and investigational product blinded carton number. Unblinded site staff will prepare and administer investigational product. Please refer to the SRM under separate cover for further instruction on this process.
- Collect a blood sample of approximately 20 mL for immunogenicity testing ([Section 7.2](#)).
- Investigational product will be administered by intramuscular injection, by the unblinded administrator, into the upper deltoid muscle, preferably of the nondominant arm.
- The unblinded vaccine administrator updates the investigational product accountability records.
- Blinded study staff will observe the subject for at least 30 minutes after investigational product administration for any acute reactions. Any AEs noted during the observation period should be recorded as immediate AEs.
- Record and report AEs and SAEs (relative to the time of vaccination) as described in [Section 8](#) and the [Schedule of Activities](#).
- Issue a measuring device for measurement of local reactions, and a digital thermometer for recording of daily temperatures, and provide instructions on their use.
- Issue a subject e-diary and provide instructions on its completion. Ask the subject to complete the e-diary from Day 1 to Day 14, with Day 1 being the day of vaccination.
- Ask the subject to contact the site staff or investigator immediately, to determine if an unscheduled visit is required, if he or she experiences any of the following:
  - Fever  $\geq 39.0^{\circ}\text{C}$  ( $\geq 102.1^{\circ}\text{F}$ ).
  - Redness or swelling at the injection site measuring greater than 10 cm ( $\geq 21$  measuring device units).
  - Any peeling/scaling or blackening of the skin at the injection site.
  - Severe arm pain.

- Any severe systemic event within 14 days following vaccination.
- Ask the subject to contact the site staff or investigator immediately if any significant illness or hospitalization occurs.
- Schedule an appointment for the subject to return for the next study visit.
- Remind the subject to bring the completed e-diary to the next visit.
- Complete the source documents.
- Complete the CRF.

#### **6.2.2. Visit 2: Day 30 - Vaccination 2 (25 to 35 Days After Visit 1)**

- Review the subject's e-diary data and follow up on any ongoing local reactions or systemic events.
- Ensure that the subject continues to be eligible for the study and does not meet any of the withdrawal criteria as described in [Section 6.5](#).
- Based on clinical evaluation, determine whether any AEs or SAEs have occurred since the last study visit. Record and report findings as described in [Section 8](#) and the [Schedule of Activities](#). Review AEs that were ongoing from the previous visit and record their stop dates or confirm if they are still continuing.
- Record nonstudy vaccines and concomitant medications as described in [Section 5.8.1](#).
- Conduct a targeted physical examination, including vital signs if appropriate, evaluating any clinically significant abnormalities based on history and the participant's self-reported symptoms or complaints since the last visit. Abnormal results, including those that indicate worsening of medical history conditions, must be recorded on source documents and the AE CRF (with recording of time relative to vaccination) as appropriate.
- Measure and record the subject's oral temperature.
- Ensure that none of the temporary delay criteria are met ([Section 4.5](#)).
- Collect a blood sample of approximately 20 mL for immunogenicity testing ([Section 7.2](#)).
- Investigational product will be administered by intramuscular injection, by the unblinded administrator, into the upper deltoid muscle, preferably of the nondominant arm.
- The unblinded vaccine administrator updates the investigational product accountability records.

- Blinded study staff will observe the subject for at least 30 minutes after investigational product administration for any acute reactions. Any AEs noted during the observation period should be recorded as immediate AEs.
- Record and report AEs and SAEs (relative to the time of vaccination) as described in [Section 8](#) and the [Schedule of Activities](#).
- Remind the subject to complete the e-diary from Day 1 to Day 14, with Day 1 being the day of vaccination. Instruct the subject that e-diary entries for injection site symptoms should be in relation to the vaccination received that day and not to the previous vaccination.
- Ask the subject to contact the site staff or investigator immediately, to determine if an unscheduled visit is required, if he or she experiences any of the following:
  - Fever  $\geq 39.0^{\circ}\text{C}$  ( $\geq 102.1^{\circ}\text{F}$ ).
  - Redness or swelling at the injection site measuring greater than 10 cm ( $\geq 21$  measuring device units).
  - Any peeling/scaling or blackening of the skin at the injection site.
  - Severe arm pain.
  - Any severe systemic event within 7 days following vaccination.
  - If any new, late-onset reaction occurs from the previous vaccination.
  - If any ongoing reaction from the previous vaccination worsens.
- Ask the subject to contact the site staff or investigator immediately if any significant illness or hospitalization occurs.
- Schedule an appointment for the subject to return for the next study visit.
- Complete the source documents.
- Complete the CRF.

#### **6.2.3. Visit 3: Day 37 (7 to 11 Days After Visit 2)**

- Review the subject's e-diary data and remind subjects to continue completing the e-diary up to Day 14.
- Ensure that the subject continues to be eligible for the study and does not meet any of the withdrawal criteria as described in [Section 6.5](#).

- Based on clinical evaluation, determine whether any AEs or SAEs have occurred since the last study visit. Record and report findings as described in [Section 8](#) and the [Schedule of Activities](#). Review AEs that were ongoing from the previous visit and record their stop dates or confirm if they are still continuing.
- Record nonstudy vaccines and concomitant medications as described in [Section 5.8.1](#).
- Conduct a targeted physical examination, including vital signs if appropriate, evaluating any clinically significant abnormalities based on history and the participant's self-reported symptoms or complaints since the last visit. Abnormal results, including those that indicate worsening of medical history conditions, must be recorded on source documents and the AE CRF (with recording of time relative to vaccination) as appropriate.
- Collect a blood sample of approximately 20 mL for immunogenicity testing ([Section 7.2](#)).
- Ask the subject to contact the site staff or investigator immediately if he or she experiences any of the following:
  - Fever  $\geq 39.0^{\circ}\text{C}$  ( $\geq 102.1^{\circ}\text{F}$ ).
  - Redness or swelling at the injection site measuring greater than 10 cm ( $\geq 21$  measuring device units).
  - Any peeling/scaling or blackening of the skin at the injection site.
  - Severe arm pain.
  - Any severe systemic event within 14 days following vaccination to determine if an unscheduled visit is required.
  - If any new, late-onset reaction occurs from the previous vaccination.
  - If any ongoing reaction from the previous vaccination worsens.
- Ask the subject to contact the site staff or investigator immediately if any significant illness or hospitalization occurs.
- Schedule an appointment for the subject to return for the next study visit.
- Remind the subject to bring the completed e-diary to the next visit.
- Complete the source documents.
- Complete the CRF.

#### **6.2.4. Visit 4: Month 2 (25 to 35 Days After Visit 2)**

- Review the subject's e-diary data after Dose 2 and follow up on any ongoing local reactions or systemic events.
- Ensure that the subject continues to be eligible for the study and does not meet any of the withdrawal criteria as described in [Section 6.5](#).
- Based on clinical evaluation, determine whether any AEs or SAEs have occurred since the last study visit. Record and report findings as described in [Section 8](#) and the [Schedule of Activities](#). Review AEs that were ongoing from the previous visit and record their stop dates or confirm if they are still continuing.
- Record nonstudy vaccines and concomitant medications as described in [Section 5.8.1](#).
- Conduct a targeted physical examination, including vital signs if appropriate, evaluating any clinically significant abnormalities based on history and the participant's self-reported symptoms or complaints since the last visit. Abnormal results, including those that indicate worsening of medical history conditions, must be recorded on source documents and the AE CRF (with recording of time relative to vaccination) as appropriate.
- Collect a blood sample of approximately 20 mL for immunogenicity testing ([Section 7.2](#)). An additional blood sample of approximately 40 mL will be obtained.
- Ask the subject to contact the site staff or investigator immediately if any significant illness or hospitalization occurs.
- Schedule an appointment for the subject to return for the next study visit.
- Complete the source documents.
- Complete the CRF.

#### **6.2.5. Visit 5: Month 6 - Vaccination 3 (135 to 165 Days After Visit 2)**

- Ensure that the subject continues to be eligible for the study and does not meet any of the withdrawal criteria as described in [Section 6.5](#).
- Based on clinical evaluation, determine whether any AEs or SAEs have occurred since the last study visit. Record and report findings as described in [Section 8](#) and the [Schedule of Activities](#). Review AEs that were ongoing from the previous visit and record their stop dates or confirm if they are still continuing.
- Record nonstudy vaccines and concomitant medications as described in [Section 5.8.1](#).
- Conduct a targeted physical examination, including vital signs if appropriate, evaluating any clinically significant abnormalities based on history and the participant's

self-reported symptoms or complaints since the last visit. Abnormal results, including those that indicate worsening of medical history conditions, must be recorded on source documents and the AE CRF (with recording of time relative to vaccination) as appropriate.

- Measure and record the subject's oral temperature.
- Ensure that none of the temporary delay criteria are met ([Section 4.5](#)).
- Collect a blood sample of approximately 20 mL for immunogenicity assessments ([Section 7.2](#)).
- Investigational product will be administered by intramuscular injection, by the unblinded administrator, into the upper deltoid muscle, preferably of the nondominant arm. The unblinded vaccine administrator updates the investigational product accountability records.
- Blinded study staff will observe the subject for at least 30 minutes after investigational product administration for any acute reactions. Any AEs noted during the observation period should be recorded as immediate AEs.
- Record and report AEs and SAEs (relative to the time of vaccination) as described in [Section 8](#) and the [Schedule of Activities](#).
- Remind the subject to complete the e-diary from Day 1 to Day 14, with Day 1 being the day of vaccination. Instruct the subject that e-diary entries for injection site symptoms should be in relation to the vaccination received that day and not to the previous vaccination.
- Ask the subject to contact the site staff or investigator immediately, to determine if an unscheduled visit is required, if he or she experiences any of the following:
  - Fever  $\geq 39.0^{\circ}\text{C}$  ( $\geq 102.1^{\circ}\text{F}$ ).
  - Redness or swelling at the injection site measuring greater than 10 cm ( $\geq 21$  measuring device units).
  - Any peeling/scaling or blackening of the skin at the injection site.
  - Severe arm pain.
  - Any severe systemic event within 7 days following vaccination.
  - If any new, late-onset reaction occurs from the previous vaccination.
  - If any ongoing reaction from the previous vaccination worsens.

- Ask the subject to contact the site staff or investigator immediately if any significant illness or hospitalization occurs.
- Schedule an appointment for the subject to return for the next study visit.
- Remind the subject to bring the completed e-diary to the next visit.
- Complete the source documents.
- Complete the CRF.

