#### **6.1.3. Visit 3: Day 15 (7 to 11 Days After Visit 2)**

- Review the subject's e-diary data and remind the subject to continue completing the e-diary up to Day 14.
- Ensure that the subject continues to be eligible for the study and does not meet any of the withdrawal criteria as described in [Section 6.5](#).
- Based on clinical evaluation, determine whether any AEs or SAEs have occurred since the last study visit. Record and report findings as described in [Section 8](#) and the [Schedule of Activities](#). Review AEs that were ongoing from the previous visit and record their stop dates or confirm if they are still continuing.
- Record nonstudy vaccines and concomitant medications as described in [Section 5.8.1](#).
- Conduct a targeted physical examination, including vital signs if appropriate, evaluating any clinically significant abnormalities based on history and the participant's self-reported symptoms or complaints since the last visit. Abnormal results, including those that indicate worsening of medical history conditions, must be recorded on source documents and the AE CRF (with recording of time relative to vaccination) as appropriate.
- Collect a blood sample of approximately 20 mL for immunogenicity testing ([Section 7.2](#)).
- Ask the subject to contact the site staff or investigator immediately, to determine if an unscheduled visit is required, if he or she experiences any of the following:
  - Fever  $\geq 39.0^{\circ}\text{C}$  ( $\geq 102.1^{\circ}\text{F}$ ).
  - Redness or swelling at the injection site measuring greater than 10 cm ( $\geq 21$  measuring device units).
  - Any peeling/scaling or blackening of the skin at the injection site.
  - Severe arm pain.

- Any severe systemic event within 14 days following vaccination.
- If any new, late-onset reaction occurs from the previous vaccination.
- If any ongoing reaction from the previous vaccination worsens.
- Ask the subject to contact the site staff or investigator immediately if any significant illness or hospitalization occurs.
- Schedule an appointment for the subject to return for the next study visit.
- Remind the subject to bring the completed e-diary to the next visit.
- Complete the source documents.
- Complete the CRF.

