#### **6.2.6. Visit 6: Day 187 (7 to 11 Days After Visit 5)**

- Review the subject's e-diary data and remind subjects to continue completing the e-diary up to Day 14.
- Ensure that the subject continues to be eligible for the study and does not meet any of the withdrawal criteria as described in [Section 6.5](#).
- Based on clinical evaluation, determine whether any AEs or SAEs have occurred since the last study visit. Record and report findings as described in [Section 8](#) and the [Schedule of Activities](#). Review AEs that were ongoing from the previous visit and record their stop dates or confirm if they are still continuing.
- Record nonstudy vaccines and concomitant medications as described in [Section 5.8.1](#).
- Conduct a targeted physical examination, including vital signs if appropriate, evaluating any clinically significant abnormalities based on history and the participant's self-reported symptoms or complaints since the last visit. Abnormal results, including those that indicate worsening of medical history conditions, must be recorded on source documents and the AE CRF (with recording of time relative to vaccination) as appropriate.
- Collect a blood sample of approximately 20 mL for immunogenicity testing ([Section 7.2](#)).
- Ask the subject to contact the site staff or investigator immediately if any significant illness or hospitalization occurs.
- Schedule an appointment for the subject to return for the next study visit.
- Remind the subject to bring the completed e-diary to the next visit.
- Complete the source documents.
- Complete the CRF.

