#### **6.2.7. Visit 7: Month 7 (25 to 35 Days After Visit 5)**

- Review the subject's e-diary data after Dose 3 and follow up on any ongoing local reactions or systemic events.
- Collect the subject's e-diary.
- Ensure that the subject continues to be eligible for the study and does not meet any of the withdrawal criteria as described in [Section 6.5](#).
- Based on clinical evaluation, determine whether any AEs or SAEs have occurred since the last study visit. Record and report findings as described in [Section 8](#) and the [Schedule of Activities](#). Review AEs that were ongoing from the previous visit and record their stop dates or confirm if they are still continuing.
- Record nonstudy vaccines and concomitant medications as described in [Section 5.8.1](#).
- Conduct a targeted physical examination, including vital signs if appropriate, evaluating any clinically significant abnormalities based on history and the participant's self-reported symptoms or complaints since the last visit.
- Collect a blood sample of approximately 20 mL for immunogenicity testing ([Section 7.2](#)).
- Ask the subject to contact the site staff or investigator immediately if any significant illness or hospitalization occurs.
- Schedule an appointment for the subject to return for the next study visit.
- Complete the source documents.
- Complete the CRF.

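### Month 0, 1, 6 regimen, Dose 3: the diary runs 14 days, but subjects are told to call about severe systemic events for only 7, and Visit 6 does not correct this

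*Protocol*

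**What the plan says.** At the third vaccination of the Month 0, 1, 6 regimen (Protocol section 6.2.5), site staff are told: "Remind the subject to complete the e-diary from Day 1 to Day 14, with Day 1 being the day of vaccination". The same section lists the events for which the subject should contact the site at once. For systemic events other than fever, the entry is "Any severe systemic event within 7 days following vaccination".

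Visit 6 (section 6.2.6) takes place 7 to 11 days after that dose. Staff must "remind subjects to continue completing the e-diary up to Day 14", so the protocol treats the diary period as still open. The list of severe reactions and events is not repeated there. The only contact instruction is "Ask the subject to contact the site staff or investigator immediately if any significant illness or hospitalization occurs". Visit 7 (section 6.2.7) follows 25 to 35 days after the dose.

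Elsewhere the follow-up visit restates the list with the longer window. Section 6.1.3 (Day regimen, after Dose 2) has "Any severe systemic event within 14 days following vaccination", and section 6.2.3 (Month regimen, after Dose 2) has "Any severe systemic event within 14 days following vaccination to determine if an unscheduled visit is required".

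**The concern.** In the rest of the protocol the period in which a subject should call about a severe systemic event matches the diary period, at the latest from the follow-up visit onward. Month-regimen Dose 3 breaks that pattern, and the protocol gives no reason.

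What is at stake is one route to prompt assessment, the subject's own call, in adults aged 65 to 85. The route matters somewhat more for systemic than for local events. Section 7.1.1.2 says a subject with a severe local reaction will be prompted to contact the investigator, and section 7.1.1.3 has no equivalent sentence for systemic events. For severe headache, fatigue, vomiting, diarrhea, and muscle or joint pain, the visit instruction is therefore the main subject-initiated route.

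**Working it through.** There is no planned figure to reproduce. The check sets diary length against call-in window for every dose, then counts days.

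**Dose by dose** (Protocol sections 6.1 to 6.3; call-in window for severe systemic events)

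| Dose | Diary | At vaccination | At the visit 7 to 11 days later |
|---|---|---|---|
| Day regimen, Dose 1 | 7 days | 7 days (6.1.1) | next visit is Dose 2 |
| Day regimen, Dose 2 | 14 days | 7 days (6.1.2) | 14 days (6.1.3) |
| Day regimen, Dose 3 | 14 days | 14 days (6.1.4) | 14 days (6.1.5) |
| Month regimen, Dose 1 | 14 days | 14 days (6.2.1) | no such visit |
| Month regimen, Dose 2 | 14 days | 7 days (6.2.2) | 14 days (6.2.3) |
| Month regimen, Dose 3 | 14 days | 7 days (6.2.5) | list absent (6.2.6) |
| Extension, Dose 4 | 14 days | 14 days (6.3.1) | 14 days (6.3.2) |

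Six doses have a 14-day diary, and five of them receive a 14-day instruction at one visit or the other. Five visits fall 7 to 11 days after such a dose (6.1.3, 6.1.5, 6.2.3, 6.2.6, 6.3.2), and four carry the list. The one dose with a 7-day window and no later extension, Day-regimen Dose 1, also has a 7-day diary, so its window matches.

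**Could other entries in section 6.2.5 fill the gap?** The entries on late-onset and worsening reactions refer to the previous vaccination. Section 6.2.5 itself tells subjects to make injection-site entries "in relation to the vaccination received that day and not to the previous vaccination", so in that section the previous vaccination means the earlier dose. These entries are not counted as covering Dose 3. Fever, redness or swelling, skin change and severe arm pain have no time limit and are unaffected.

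**Days without an explicit instruction.** Diary Day 1 is the vaccination day, so 7 days after vaccination is diary Day 8.
- Days 9 to 14: 14 − 8 = 6 days; 6/14 = 43%.
- If 7 days means diary Days 1 to 7, then Days 8 to 14: 14 − 7 = 7 days; 7/14 = 50%.

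**Days left after Visit 6.** Visit 6 falls on diary Day 8 to 12. Days remaining: 14 − 8 = 6 down to 14 − 12 = 2, or 43% to 14% of the diary. Events that began before Visit 6 are assessed at Visit 6.

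**Longest plausible delay.** Visit 7 falls on diary Day 26 to 36. A subject would wait until then mainly if the event began after Visit 6, had resolved before the last diary day (taken as Day 14), and was missed on diary review. That puts onset on Day 9 to 13. Shortest wait: 26 − 13 = 13 days. Longest: 36 − 9 = 27 days.

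**Subjects given this wording.** 183 + 183 + 61 = 427 randomized to the Month regimen (Table 1). If the 12% maximum dropout in section 9.1 all occurred before Dose 3, which is an assumption, 0.88 × 427 = 375.8, about 376.

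**The case against.** The strongest reply is that the gap is largely covered elsewhere.
- Section 6.4 requires prompt telephone contact for any severe systemic event reported between visits, without a 7-day limit. Its exception for mistaken diary entries implies that a diary entry counts as a report.
- Section 7.1.1 gives investigators and sponsor clinicians continuous access to diary data, requires frequent review, and requires the site to contact the subject about events still ongoing on the last diary day.
- Section 7.1.1.3 asks subjects to report events that persist beyond the diary period.
- The undated illness instruction plausibly reaches some Grade 3 events, such as vomiting that needs intravenous fluids (Table 3).
- Under section 6.4 no site visit is needed once the reaction has gone, so in the residual case the delay is mainly to a telephone call.

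All of this stands, and it is why the point is minor. It does not replace the instruction. Section 6.4 acts only once an event is reported, the review interval in section 7.1.1 is not defined, and a subject may not regard severe fatigue or joint pain as a significant illness.

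A second reply is that Day-regimen Dose 2 and Month-regimen Dose 2 also say 7 days at vaccination. That is correct, and until the follow-up visit all three doses share the same wording gap. What is peculiar to Month-regimen Dose 3 is the 2 to 6 days after Visit 6, because only there is the window never extended.

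A third reply concerns timing. Amendment 2 adds a blood draw at Visit 12, about 18 months after Dose 3 (12 months to Dose 4, then 6 more), so Dose 3 vaccinations may already have been complete or nearly so. The documents give no enrollment dates, so this cannot be settled. If it is so, the value lies in the wording carried into later protocols.

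**Conclusion.** The concern holds as a minor safety-consistency correction. Month-regimen Dose 3 is the only one of six doses with a 14-day diary that never receives a 14-day call-in instruction for severe systemic events. The pattern points to a missed edit, not a choice.

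The gap is 6 of 14 diary days, or 7 on the stricter reading, of which the 2 to 6 days after Visit 6 are specific to this dose. The 13-to-27-day wait applies only to the residual case described above. The 427 (or about 376) subjects are those given the wording, not those expected to have an event. The documents give no rate of late-onset severe systemic events, so no expected number can be stated.

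The diary still records these events for all 14 days, so endpoints, analyses and within-regimen comparisons are unaffected. So is the triggered review rule, which concerns erythema. A Grade 3 systemic event does not stop vaccination under section 6.5 or 7.1.1.3. The subject-facing materials outside these documents were not available, so what subjects were actually told could not be checked.

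**What to change.** In section 6.2.5, change the window for severe systemic events from 7 to 14 days. In section 6.2.6, insert the contact list already used at the corresponding Day-regimen visit (section 6.1.5), with its 14-day window. Either edit alone would give this dose a 14-day instruction. Making both aligns the vaccination visit with the diary and Visit 6 with the other four follow-up visits of its kind.

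The same one-number change could be made in sections 6.1.2 and 6.2.2 for tidiness, but it is not needed here because sections 6.1.3 and 6.2.3 already extend the window.

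The cost is one number and one copied list, plus perhaps a few more subject calls. No analysis, sample size or SAP text changes.
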